Standard procedures will be employed to see that the delivery of the study therapy and the collection of study data are separated. The Evaluative Component and Clinical Trial Component will be carried out by a different staff member for each Veteran. After the data collector completes the assessments of the Veteran eligible for randomization, the data collector will enter the information for urn randomization into the computer program, but the study therapist will actually give the software command to conduct the urn randomization and generate group assignment. All outcome evaluations will be conducted by the data collector, and Veterans will be asked not to tell the data collector whether SBIRT was delivered. In summary, the clinical trial is not adversely impacted by the presence of a preceding Evaluative Component.

It also is unlikely that the Evaluative Component will not be interpretable because of the Clinical Trial Component. The 480 Veterans who are not randomized (because they do not have risky alcohol use and/or substance use) will be compared to the 80 substance users randomized to No-Additional-Treatment, using a prospective observational design to determine effects of substance use. Both groups will receive serial assessments that are not likely to impact outcomes.

2. Power Analysis for Analysis of the Effects of Substance Use on Outcomes: The effects of substance abuse on outcomes will be analyzed by random effects regression analyses. The treatment attendance outcome will yield a value for each week (attendance or not) and PTSD severity will be assessed at three time points (baseline, 4 and 12 weeks). In the primary analysis, these repeated-measures outcomes will be regressed on substance use, with covariates included that represent potentially confounding differences between Veterans with and without substance use disorders. The proposed sample of 560 participants receiving No-Additional-Treatment, of whom 80 are substance users, has power  $> .80$  to detect standardized mean differences in linear slopes as small as  $\delta = .25$ , allowing for potential downward bias in effects from nonrandom group assignment (Optimal Design software version 1.77), and partial  $\eta^2$  of  $< .1$ , correcting for non-sphericity (G\*Power 3.1.2, Buchner et al., 1992-2009).

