**C. Single Patient Flow Chart**

\_\_\_\_\_ Veteran receives mailed letter explaining that a telephone call will be coming and allowing the Veteran to opt-out of receiving it

\_\_\_\_\_ Telephone call inviting participation. The research assistant asks the Veteran questions to determine eligibility. Following a script, the research assistant describes the study to the Veteran and schedules an appointment for informed consent and baseline data collection. Appointments will be scheduled on the day of the Compensation examination or up to two weeks before it.

\_\_\_\_\_ Informed consent

\_\_\_\_\_ Evaluative Component: Data collector conducts assessment. If the Veteran meets the substance use and other criteria for randomization, the data collector contacts Dr.

[name] (or her back-up) with the information [name] needs to conduct the urn randomization.

\_\_\_\_\_ Randomization and Scheduling of Next Appointments: The data collector arranges for the Veteran to telephone [name] in a separate room from the research assistant. The data collector asks the Veteran not to tell him/her about any appointments other than the four week follow-up visit.

[name] tells Veterans randomized to SBIRT about the assignment and explains how to make contact with the study therapist. This will happen by all of the following that the Veteran agrees to and/or are feasible: (1) giving the Veteran the therapist's name and telephone number, (2) giving the therapist the Veteran's name and telephone number, (3) giving the Veteran directions to the therapist's office to schedule an appointment. Therapists will schedule therapy sessions immediately after the Compensation exam if feasible and if not, will offer times in the subsequent two weeks.

Regardless of what condition the Veteran is randomized to, [name] will schedule the Veteran's week 4 follow-up appointment with the data collector using a shared online calendar (but no client identifiers).

- \_\_\_\_\_ Veteran undergoes standard Compensation examination
- \_\_\_\_\_ Substance use patients randomized to SBIRT receive counseling.
- \_\_\_\_\_ Weeks 4 and 12: Data collector administers assessments

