#### G. Assessments

1. Separation of Therapies from Assessments: Veterans will be instructed during the assessments not to tell the research assistant if they are receiving study counseling. To determine if the blind was maintained, we will ask the research assistant to rate for each client the condition the Veteran was assigned to and the research assistant's certainty about the randomization on a 0-100 visual analogue scale with 0 being no certainty and 100 being absolute certainty.

2. Data Collection Procedures: Participants will be asked at the beginning of enrollment for the names and telephone numbers of three people who can find them if the research assistant has difficulty reaching them over the course of study participation. Within two days of an upcoming appointment, participants will receive a reminder call and/or a short message service reminder (text message). If a participant misses a scheduled appointment, the research assistant will call to reschedule. If the participant cannot be reached, staff will call up to three identified contacts to locate the participant.

Research staff will call the Veteran up to three times over a three week period. If, after talking to a contact, the research staff member learns that there is another telephone number that should be used to reach the patient, that number will be called up to twice over a two-week period.

3. Location: Research staff may offer to meet Veterans at a convenient location for data collection visits, including Veteran Centers, local VA clinics, or public places. These visits will occur in a private room and this arrangement will be verified in advance of the visit with both the participant and the facility. Research staff will keep identifiable patient information and study data in separate folders. All information will be transported by research staff in a locked bag and will be brought directly back to the VA for filing after study visits.

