9. The Response to Stressful Experiences Scale contains 22-items describing the respondent's characteristic methods for dealing with stressful experiences. Each item is rated on a 5-point scale indicating the extent to which the item describes a method used by the respondent. Variability among participants in the availability and use of methods to deal with stressful experiences has accounted for variance in severity of PTSD symptoms in military samples (Johnson, Polusny, Erbes et al., 2011).

11. Self-Reported Service Use: A timeline-follow-back method will be used to determine service use during the preceding 60 days. An important benefit of this approach over summary measures is that it minimizes problems associated with information being collected twice for the same service, such as detoxification counted as a medical hospitalization and as substance abuse treatment, and it minimizes problems associated with overlapping data points. The questions about service use will be drawn from the Treatment Services Review (McLellan, Alterman et al. 1992) and the Program and Client Cost-Substance Abuse Treatment (PACC-SAT). The Treatment Services Review includes inquiries about each of the 7 domains explored in the Addiction Severity Index. The PACC-SAT was adapted from the DATCAP and involves questions about different types of services received.

The Service Use calendar has been modified to address analyses that will be conducted in the proposed studies. Specifically, the data collector will code services by non-substance use providers by whether they addressed substance abuse. As shown in the chart review of OEF/OIF Veterans who sought Compensation at VA Connecticut, more OEF/OIF Veterans with PTSD claims received mental health services than specialty substance abuse services. However, VA service use data cannot be used to determine whether people with substance use problems are having those issues addressed if they attend mental health treatment. Therefore, the service use calendar we will be using for self-reported treatment attendance includes inquiries concerning whether substance abuse was addressed during other mental health treatment.

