## 12. Process Measures:

a. A three-item Motivation for Change scale will be used that taps alcohol or drug use likelihood ("How likely are you to use alcohol or drugs, even a little, ever again?") problem recognition ("How big of a problem is your drug use?"), and treatment motivation ("How interested are you in treatment right now?"). Respondents answer each item using an analogue scale coded from 1 to 100. Scores for the three items are averaged after reverse scoring for the drug-use likelihood item. This simple scale has been sensitive to change in a clinical trial

(Ondersma, Svikis et al. 2007) and a similar scale predicted behavior change in an observational study (LaBrie, Quinlan et al. 2005). Stage of Change measures are of interest because they are one mechanism by which SBIRT may operate. The relationship between Stage of Change and outcome has not been consistent because stage of change is confounded with illness severity but appears to change with brief Motivational Interviewing interventions (Dunn and Ries 1997).

b. Satisfaction with Counseling will be rated on Likert-scaled items that are combined to yield a composite score. *Veterans will be asked to indicate their satisfaction with the amount of attention to PTSD on a Likert-scale anchored by "too much" and "too little."* The ratings form will be handed to the Veteran, placed in a sealed envelope, and sent to the data manager.

c. Qualitative data concerning the impact of study participation on the examination will be obtained during the week 4 evaluation, first with an open-ended probe: "Tell me any ways the assessment you completed four weeks ago affected you later." Follow-up probes will address whether the CAPS interview impacted the C&P exam specifically, and whether Veterans believed study participation impacted their service-connection evaluation.

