## 2. Safety Monitoring Plan:

Participants in Evaluative Component: The risk to Veterans participating in the Evaluative Component who only receive assessments and are not randomized to SBIRT or control is minimal. Only study-related adverse events or study-related serious adverse events impacting these evaluation-only patients will be reported to [name] and if he is unavailable, to [name]. Reports to [name] will include a description of the event and a summary of recent contacts with the patient. [name] will report these to the IRB within three working days.

Participants Randomized in Clinical Trial Component: The risk to Veterans who do go on to be randomized to SBIRT or no-additional-treatment is low (greater than minimal). Veterans with PTSD have a high frequency of medical and psychiatric difficulties. Therefore, changes in medication regimen, the presence of medication side effects and symptom exacerbations are not untoward and do not constitute adverse events. Anticipated adverse events include complaints about the study procedures and the counseling, and any occurrence in which the patient attributes discomfort, harm or disability to the study procedures.

In the clinical trial, assessment for adverse events will be a routine part of every study and therapy visit. SAEs and AEs will be screened for in the timeline follow-backs. Any report that a patient required overnight treatment in any facility (emergency room, detoxification, and hospitalization) will constitute an SAE, as will any report of death or serious disability. Hospitalization or death of another individual due to direct action of patient will also be considered an SAE. When an AE or SAE is reported by a participant, we will refer to the medical chart for additional information.

Any SAEs will be immediately reported to [name] and, if he is unavailable, to [name]. Reports to [name] will include a description of the event and a summary of recent contacts with the patient. This summary will include any warning signs of the adverse event, the patient's general state and any information suggesting a causal link between study participation and the event. [name] will report these to the IRB within 3 working days.

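### The masked CAPS rater also takes a week-4 service history whose window always contains the SBIRT session, and study counseling is not excluded from it

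*Combined protocol and SAP*

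**What the plan says.** **Who assesses.** The section justifying the combined design states: "All outcome evaluations will be conducted by the data collector, and Veterans will be asked not to tell the data collector whether SBIRT was delivered". The Single Patient Flow Chart has the entry "Weeks 4 and 12: Data collector administers assessments". The PTSD Assessments section gives the CAPS interview to a data collector.

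**What protects the blind.** Therapy and assessment are done by different staff, and the Veteran hears the assignment by telephone in a separate room. The flow chart adds: "The data collector asks the Veteran not to tell him/her about any appointments other than the four week follow-up visit". Under G. Assessments, item 1, "Veterans will be instructed during the assessments not to tell the research assistant if they are receiving study counseling". That item also provides a check: "To determine if the blind was maintained, we will ask the research assistant to rate for each client the condition" to which the Veteran was assigned, with a certainty score from 0 to 100. Satisfaction with counseling goes to the data manager in a sealed envelope (Process Measures, item b).

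**What the same person must ask.** The Schedule of Assessments places the Service Use Calendar at baseline, week 4 and week 12, the same visits as the CAPS and the Substance Use Calendar. Under Self-Reported Service Use (item 11) the calendar covers the preceding 60 days, and "the data collector will code services by non-substance use providers by whether they addressed substance abuse". It also records non-VA care. In the Safety Monitoring Plan, "assessment for adverse events will be a routine part of every study and therapy visit"; the timeline follow-backs are used for this screening, and complaints about the counseling are among the anticipated events. At week 4 there is also an open-ended probe: "Tell me any ways the assessment you completed four weeks ago affected you later".

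**The concern.** An SBIRT Veteran at week 4 has been told not to mention study counseling. The person who must not know then takes that Veteran through a dated service history that covers the counseling, and asks whether providers outside substance abuse care addressed substance use. The SBIRT session fits that description. A complete answer discloses the arm. Obeying the instruction leaves the calendar incomplete, by a rule that each Veteran has to work out alone. A control Veteran has no such session to report.

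The main stake is the CAPS. It depends on the rater's judgment, and its total score is also the mediator tested in section K.3. What a rater learns at week 4 is still known when the week-12 CAPS is scored, and the analysis cannot remove it.

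A smaller stake is under-reporting. A Veteran who reads the flow-chart instruction broadly may leave out genuine visits. VA visits come from administrative databases, so the only data at risk are non-VA weeks in the attendance outcome and the record of whether substance abuse was addressed.

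**Working it through.** The plan gives no figure to reproduce here. The one arithmetic question is whether the 60-day look-back reaches the SBIRT session.

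Inputs:
- Follow-up visits are four and twelve weeks after the examination: days 28 and 84 (Specific Aims).
- The SBIRT session is 0 to 14 days after the examination: 15 possible days (justification for flexible scheduling).
- The look-back is 60 days (Self-Reported Service Use).

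Formula: session age = visit day − session day. The session is in the window if its age is at most 60.

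| Visit | Session age in days | Days inside the window |
|---|---|---|
| Week 4 | 28 − 14 = 14 to 28 − 0 = 28 | 15 of 15 |
| Week 12 | 84 − 14 = 70 to 84 − 0 = 84 | 0 of 15 |

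Sensitivity: suppose visits were counted from baseline, which may be 0 to 14 days before the examination. The session then falls 0 to 28 days after baseline, with 15 × 15 = 225 combinations of days.
- Week 4: age 0 to 28, always inside (225 of 225).
- Week 12: age 56 to 84, inside only if the session is at least 24 days after baseline. That gives 5 + 4 + 3 + 2 + 1 = 15 of 225 combinations. This counts combinations and is not a probability.

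The week-4 result therefore holds under either anchor. The week-12 calendar does not reach the session under the stated anchor, and reaches it only at the margin under the other.

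How many are exposed: at most the 80 Veterans assigned to SBIRT, and none of the 80 controls. If attendance matched the 96% in the vocational counseling study cited under Feasibility, 0.96 × 80 = 76.8, about 77, would have a session to report. That rate is borrowed from a different intervention.

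The other instruments, set against the masking instruction:
- *Adverse events.* Screening takes place at every study visit with no stated look-back limit. Only SBIRT Veterans can complain about study counseling. This route is open at weeks 4 and 12.
- *Week-4 probe.* It refers to the assessment four weeks earlier, which is the baseline battery. One follow-up asks whether study participation affected the service-connection evaluation. An SBIRT Veteran might mention the session in reply, but is not asked about it.
- *Arm guess.* It measures whether the blind held but does not protect it, and section K gives no use for the result.

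**The case against.** The strongest reply is that the plan has taken masking seriously. Staff are separated, assignment is given out of earshot, satisfaction forms are sealed, and the reminder not to disclose is given during the very sessions in which the calendar is completed. On that reading Veterans are already told to leave the session out, and the calendar's actual wording is not in the documents. This is fair, and it is why disclosure is a risk and not a fact. What remains is that the calendar, as described, carries no exclusion, and that a general request for silence is not a rule for completing a service history.

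A reader might infer more than the documents support:
- *That the non-disclosure request is the sole safeguard.* The other measures above show that it is not.
- *That the calendar asks for every service.* The text speaks of different types of services and neither includes nor excludes study counseling.
- *That the week-12 calendar elicits the session directly.* On the stated anchor it cannot.
- *That the first primary outcome is equally exposed.* Substance use is a self-reported daily calendar from Veterans who know their own arm. Masking the interviewer does not remove that reporting bias, and interviewer influence on day counts is a weaker argument than influence on CAPS ratings.
- *That the bias can be expressed as a share of the 0.50 effect in the power analysis.* That effect is set for treatment attendance and substance use. No CAPS effect is planned for the trial, so the comparison has no meaning for the outcome at issue.

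**Conclusion.** The point holds as a limited but real weakness. At week 4 the service-use interview always spans the SBIRT session, is conducted by the masked CAPS rater, and has no exclusion for study counseling, so a complete answer and the masking instruction conflict. Adverse-event screening is a second route at both visits. Week 12 is exposed through that screening and through anything learned at week 4, not through the calendar itself.

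The consequence falls mainly on the CAPS. The likelihood of disclosure and the size of any rating bias cannot be derived from the documents, and none is claimed. The conclusion assumes that data collector and research assistant are the same role, as the plan's usage suggests, that this person does the adverse-event screening at study visits, and that a Veteran normally sees the same one at both follow-ups. The change is worth making because it costs almost nothing and the damage, once done, cannot be repaired in the analysis.

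**What to change.** 1. Script the follow-up Service Use Calendar with the phrase 'not counting any visit or call with study staff', and tell Veterans in the same sentence to report all other VA and non-VA care. Take SBIRT delivery from the therapist contact log (section I, item 4), which already records each contact.
2. Fix the order of each follow-up visit: CAPS and Substance Use Calendar, then Service Use Calendar, then the probe (week 4 only), then adverse events, then the arm guess.
3. Keep full solicitation of adverse events, including complaints about counseling. Ask about them after the ratings, or route counseling complaints to the site investigator. Do not apply the study-staff exclusion to this question: the Safety Monitoring Plan expects these complaints, and SBIRT is a single session with no later planned therapist visit to elicit them. Because that plan screens for events within the timeline follow-backs, its wording needs to be aligned with the new order.

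The cost is a script and a fixed visit order, with no added staff and no loss of trial data. Two limits remain. Ordering protects the ratings within a visit but does not undo knowledge carried from week 4 to week 12, and visits that follow an SBIRT referral may still hint at the arm.

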## 12. Process Measures:

a. A three-item Motivation for Change scale will be used that taps alcohol or drug use likelihood ("How likely are you to use alcohol or drugs, even a little, ever again?") problem recognition ("How big of a problem is your drug use?"), and treatment motivation ("How interested are you in treatment right now?"). Respondents answer each item using an analogue scale coded from 1 to 100. Scores for the three items are averaged after reverse scoring for the drug-use likelihood item. This simple scale has been sensitive to change in a clinical trial

(Ondersma, Svikis et al. 2007) and a similar scale predicted behavior change in an observational study (LaBrie, Quinlan et al. 2005). Stage of Change measures are of interest because they are one mechanism by which SBIRT may operate. The relationship between Stage of Change and outcome has not been consistent because stage of change is confounded with illness severity but appears to change with brief Motivational Interviewing interventions (Dunn and Ries 1997).

b. Satisfaction with Counseling will be rated on Likert-scaled items that are combined to yield a composite score. *Veterans will be asked to indicate their satisfaction with the amount of attention to PTSD on a Likert-scale anchored by "too much" and "too little."* The ratings form will be handed to the Veteran, placed in a sealed envelope, and sent to the data manager.

c. Qualitative data concerning the impact of study participation on the examination will be obtained during the week 4 evaluation, first with an open-ended probe: "Tell me any ways the assessment you completed four weeks ago affected you later." Follow-up probes will address whether the CAPS interview impacted the C&P exam specifically, and whether Veterans believed study participation impacted their service-connection evaluation.

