**Either risky alcohol use OR self-reported use of an illicit drug within the last 28 days.**

- Risky alcohol use will be defined by standard criteria: >14 drinks/week or >4 drinks/occasion for men 65 or younger; >7 drinks/week or >3 drinks/occasion for women (Saitz 2005). A standard drink will be 0.5 oz of absolute alcohol, equivalent to 10 oz of beer, 4 oz of wine, or 1 oz of 100-proof liquor
- Self-reported use of an illicit drug on at least two days in the preceding 28 days.

*Veterans who use opioids will be eligible for randomization if any of the following apply to the opioids:*

- the opioids were not prescribed to the Veteran*
- *the Veteran describes obtaining the opioids from more than one provider (other than coordinated care)*
- *the Veteran endorses the SCID screening question indicating use of the drug for non-medical purposes (First, Spitzer et al. 1996)*

Veterans who use medical marijuana will be eligible for randomization. Justification: Veterans sometimes only use medical marijuana for medical reasons, sometimes use medical marijuana for reasons other than what it was prescribed for (e.g. to relax and not for pain relief), and sometimes have a medical prescription but also use marijuana from other sources. Regardless, medical marijuana use puts someone at risk for future misuse of cannabis or other drugs. Furthermore, medical marijuana is not legal in some states or federally. Randomized clients will be counseled about the risks if cannabis is used in ways other than how it is prescribed.

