#### 4. Feasibility:

a. Feasibility of Identifying People Applying for Service Connection for Compensation Exams: At both VACT and TVHS, the Compensation and Pension Clinic schedules Veterans who apply for Compensation for examinations, making this clinic an efficient place to identify potential study participants. We have established procedures to recruit Veterans presenting for Compensation examinations in our previous studies.

b. Feasibility of Enrolling 480 Veterans in the Evaluative Component:

Tennessee: During 2009, TVHS was the site for 299 initial PTSD Compensation examinations for OEF/OIF Veterans, including 22 women.

VA Connecticut: After obtaining IRB approval, our group reviewed the VA charts and Compensation examination reports of 62 consecutive OEF/OIF Veterans who underwent Compensation examinations at VA Connecticut for the six-month period between 7/1/08 and 12/31/08 to estimate rates of substance use and service use. The fact that 62 OEF/OIF Veterans presenting for new PTSD examinations were examined during a six-month period at VA Connecticut, suggests a rate of 124 per year. According to CPRS, between 5/1/12-8/1/12 there were a total of 376 mental health exams scheduled of which 117 were for people not currently service-connected.

i. A rule-out or definitive diagnosis of alcohol abuse was made in eighteen Veterans and two additional Veterans had a substance abuse diagnosis for a total of 32% with an alcohol and/or substance abuse diagnosis. This likely underestimates the rates of substance use and risky drinking because chart review is an insensitive way to identify Veterans with substance use problems (Hawkins, Kivlahan et al. 2007). Only 3% of claimants had received any substance abuse treatment at VA during the three months before the evaluation and only 47% had received any mental health treatment. Altogether, 61% were diagnosed with PTSD on the Compensation examinations and 39% were not.

These results suggest that there is a high prevalence of substance use among OEF/OIF Veterans applying for PTSD-related Compensation, an unmet need for substance abuse treatment, and a range of PTSD-symptom severities.

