### 5. Evaluation of Process Measures

Group X Time random effects regression analyses will be conducted to determine differential effects of time on Stage-of-Change, which is collected at multiple time points. The Likert-scaled therapy process ratings and other measures reflecting single values (e.g. duration of therapy sessions) will be compared between groups using ANOVAs.

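### As printed, the problem-recognition item of the Motivation for Change scale asks only about drug use, although Veterans can be randomized on risky drinking alone; the likely effect is modest dilution of one process measure

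*Combined protocol and SAP*

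**What the plan says.** Section G.12.a (Process Measures) prints three items:

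- Likelihood of use: "How likely are you to use alcohol or drugs, even a little, ever again"
- Problem recognition: "How big of a problem is your drug use"
- Treatment motivation: "How interested are you in treatment right now"

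On scoring, "Respondents answer each item using an analogue scale coded from 1 to 100", and "Scores for the three items are averaged after reverse scoring for the drug-use likelihood item". Each item therefore carries one third of the weight. The same section presents the construct as a possible mechanism of SBIRT. The Schedule of Assessments lists it, as Stage of Change, at baseline, week 4 and week 12.

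The substance criterion for randomization (section B.3) is "Either risky alcohol use OR self-reported use of an illicit drug within the last 28 days", so drinking alone qualifies. Section K.5 plans Group X Time random effects regression for "differential effects of time on Stage-of-Change, which is collected at multiple time points".

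On how common alcohol is among users, the only figure is a chart review of 62 Veterans at the Connecticut site (section B.4, Feasibility): "A rule-out or definitive diagnosis of alcohol abuse was made in eighteen Veterans and two additional Veterans had a substance abuse diagnosis".

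**The concern.** The first item covers both substances, the second covers one, and the third names none. A risky drinker with no drug use can truthfully answer about 1 to the second item however serious he or she considers the drinking to be. The scale would then record low problem recognition in someone who recognizes a problem, and that value would enter the mean with full weight. For such a Veteran, one of the three components cannot respond to SBIRT.

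Alcohol is the substance for which the Background section describes the stronger SBIRT evidence. A null result on this measure would therefore be ambiguous: SBIRT may not have changed motivation, or the item may not have asked about drinking.

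**Working it through.** **The plan's own figures.** The chart review reproduces: (18 + 2)/62 = 32.3%, against the stated 32%. The trial sample size also reproduces. For a standardized effect of .50, two-sided alpha of .05 (sidedness assumed) and power of .80, the t-test needs 63.8, so 64 per arm or 128 in total; 128/0.80 = 160. No power statement is made for the motivation scale.

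**Effect on one Veteran, read literally.** With items coded 1 to 100, reversal is taken as 101 − x (the protocol does not give the formula).

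- The maximum composite with item 2 at 1 is (100 + 1 + 100)/3 = 67, instead of 100.
- Illustration (invented answers): likelihood 90, true alcohol problem 80, treatment interest 70. If item 2 covered alcohol: (11 + 80 + 70)/3 = 53.7. As printed: (11 + 1 + 70)/3 = 27.3.

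**Share affected.** Of the 20 Veterans with a diagnosis, 18 (90%) had an alcohol diagnosis. Overlap with drug use is not reported, so 90% is an upper bound on the alcohol-only share in those charts. The share f is taken as 50% to 90%, an assumption.

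**Effect on the Group X Time contrast.** Assume equal SDs and equal treatment effects d on the three item change scores, a common correlation ρ of .2 to .6, and no change on item 2 in the share f.

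- Raw difference retained = (3 − f)/3. At f = .5 this is .833; at f = .9 it is .700.
- The variance of the summed change, in item-variance units, is v = f(2 + 2ρ) + (1 − f)(3 + 6ρ). The treated arm also gains f(1 − f)d² because the share f does not move on item 2. Averaged over the arms this adds f(1 − f)d²/2, with d = .35 assumed.
- Standardized effect retained = [(3 − f)/√(v + f(1 − f)d²/2)] ÷ [3/√(3 + 6ρ)].

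Lowest case, ρ = .2 and f = .9: v = .9 × 2.4 + .1 × 4.2 = 2.58. Adding .0055 gives 2.5855. Then (2.1/1.608)/(3/2.049) = .892.

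Highest case, ρ = .6 and f = .5: v = .5 × 3.2 + .5 × 6.6 = 4.90. Adding .0153 gives 4.915. Then (2.5/2.217)/(3/2.569) = .966.

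| ρ | f = .5 | f = .7 | f = .9 |
|---|---|---|---|
| .2 | .938 | .914 | .892 |
| .4 | .955 | .940 | .929 |
| .6 | .966 | .957 | .955 |

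The standardized loss is smaller than the raw loss because an item that does not move also contributes no variance.

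**In power terms, as illustration only.** If the full effect on this scale were .50 with 64 per arm, power by the normal approximation would be .81 undiluted and .71 to .78 across the table.

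**Partial literal reading.** If only a fraction g of alcohol-only Veterans read the item literally, f is replaced by f × g. With f = .7 and g = .5 (both assumed), the raw difference retained is (3 − .35)/3 = .883.

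**The case against.** The strongest reply is that drug use is shorthand for both substances. The scoring sentence calls the first item, which names alcohol, the drug-use likelihood item, and item 2 follows directly after it. The form itself is not in the documents, so the administered wording is unverified. This stands as a limit: nothing shows that drinkers score near the floor, and the ceiling of 67 and the example require a literal reading. It does not clear the item. The scoring sentence addresses analysts, whereas Veterans answer the printed question. A respondent who has just read of alcohol or drugs has some reason to take drug use as the narrower term. If drinkers differ in their reading, the item measures different things in different people.

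Three stronger readings are tempting, and the documents do not support them.

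- A reader might infer that alcohol-only Veterans are most of the randomized sample. The chart review does not give overlap, comes from one site, and uses a method the protocol itself calls insensitive. Trial entry rests on self-report and includes medical marijuana users and some opioid users.
- A reader might infer bias between arms. Recent illicit drug use is an urn factor, so the alcohol-only share should be similar in both arms. A shared floor shrinks the contrast without favouring either arm.
- A reader might infer a larger standardized loss. With a shift of 0.5 SD on each item, the full effect is 1.5/√(3 + 6ρ), or .73 to .58 for ρ of .2 to .6. A simulation that puts it at .50 to .60 after dilution implies a loss of 14% to 18%. That counts the standing gap between drinkers and drug users as error. Section K.5 tests change over time, so a constant gap drops out and the loss is about 3% to 11%.

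It also stands that the scale is neither a primary nor a secondary outcome, and that the only mediation model specified (section K.3) uses the CAPS.

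**Conclusion.** The point holds as a wording fault of minor severity. As printed, one third of the composite omits alcohol in a trial that randomizes on drinking alone, and no other section corrects it. Under an alcohol-only share of 50% to 90%, a fully literal reading, and item correlations of .2 to .6 (all assumed), the planned contrast would keep about 83% to 70% of its raw size and about 0.97 to 0.89 of its standardized size. A smaller share or a less literal reading reduces the loss. The consequence is a diluted and harder-to-interpret process analysis. Randomization, both primary outcomes and the sample size are unaffected.

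**What to change.** Confirm the wording on the administered form. If it is as printed, change item 2 to ask about alcohol or drug use, matching item 1, at baseline, week 4 and week 12. This costs one phrase. The small downside is a possible departure from the wording used in the cited trial in which the scale was sensitive to change.

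For data already collected with the printed wording, report the three items separately and by baseline drug use. As a sensitivity analysis, use the mean of items 1 and 3 for all Veterans. Item 2 should not be dropped only for Veterans without drug use: some would then have a two-item score and others a three-item score, which brings back the lack of comparability. The added analysis needs no new data.
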